#### **Experimental Conditions**

Only enhanced eTest participants will download the eTEST app. For these participants in the eTEST group, four HBST kits will be fit with BLE sensors and sent to participants. Follow-up calls will be made to these participants within 24 hours of opening their test to provide post-test counseling, referral for services, and a focused discussion on PrEP. In the standard HBST condition, four standard HBST kits will be sent at the same intervals, but will not be monitored and no follow-up calls will be provided. Standard participants will have a list of local resources (in Boston/Providence, L.A., or Jackson) depending on where participants are located included in the box with their test kit. This list of resources includes HIV/STD testing clinics, alcohol/drug and mental health treatment referrals, and the number for the national suicide prevention hotline,

as well as study staff contact information. These kits also, include a 24 hour helpline that participants can call with any questions or needs. In the control condition, participants will be reminded to get tested at a local clinic via text messages. Texts will link to the list of local clinics near them that conduct HIV testing, as well as their contact information/hours.

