Once users have registered, staff will conduct a brief introductory call with all participants to ensure that their information is correct and that they understand the study's requirements. After successfully completing this call, study staff will mark these participants as 'fully enrolled,' activating them in the study database. For **control** group participants, test messages will be sent to remind users when they are due to test. Tests will include a link to a web service listing nearby clinics offering HIV testing, as well as their location, phone number, hours, and cost. For **standard** HBST group participants, staff will send an HBST kit to their confirmed shipping addresses. These participants will receive no phone-based follow-up, but can use OraSure's provided 1-800 number for questions or needs. We will follow the same steps for **eTEST** participants, except that each test kit will be fit with an Estimote™ beacon. Beacons will automatically detect when each kit is opened and relay this information to a central study database, which triggers an email notification sent to counselors. Within 24 hours of opening the kit, an HIV test counselor will call **eTEST** participants to conduct post-test counseling and refer them to other needed services, including PrEP (see Section 3C.3.6.1.). HIV test counselors will be bachelor's-level staff who are certified as HIV test counselors and will have crisis intervention training. Clinical assessment and analysis of mental health will remain a responsibility of the licensed study clinician. At least one HIV test counselor will also be fluent in Spanish. Counselors will record data during each call in the study database. In each condition, participants will receive these interventions every three months over the course of the study period: at baseline, 3, 6, and 9 months.

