Online surveys will use Qualtrics and will be hosted on Brown University servers. On each quarterly survey's due date, the study database will automatically send participants an email with language-specific instructions and links to the surveys. Participants will be asked to complete these within two days, and reminder emails will be sent every other day for seven days after the due date. If participants have not completed the survey within a week of their due date, site-specific RAs will contact participants by phone, text message, and email to encourage adherence. For all participants, those who fail to complete two consecutive quarterly assessments will be considered to have withdrawn from the study. After participants complete their final online survey, they will be asked to present to designated clinics for in-person HIV testing to finish the study. Site RAs will conduct follow-up calls with participants to ensure adherence to this procedure. Study payments will be issued via a reloadable debit card that will be mailed after participants are activated in the study. Participants will earn \$25 for the baseline survey and each of the five quarterly surveys they complete, with a \$50 bonus for completing all within a week of their assignment. They will also earn an additional \$50 for completing the in-person HIV test after the study is finished, for a possible total of \$250.

Focused information/counseling on PrEP. PrEP education and counseling will take place at each post-test phone call with participants in the **eTEST** condition. During the first call, HIV test counselors will provide a brief PrEP education session, covering indications for PrEP eligibility, a description of the medication used for PrEP, and an overview of common side effects and clinical follow-up (every three months). In our past work, we have employed an effective, five minute PrEP education session during in-person HIV testing that resulted in greater PrEP awareness among MSM131, and this will guide the education delivered during HIV test counselor phone contacts. Following the education content, participants will be asked whether they are interested in making an appointment with a medical provider for PrEP consultation.

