Interested participants will be provided with contact information for the local clinical sites where PrEP is provided. During subsequent phone calls, HIV counselors will re-assess PrEP interest and provide additional information upon request. Those indicating interest in PrEP at a prior call will be asked whether they made an appointment, initiated PrEP, and have attended follow-up appointments, which will be corroborated by reviewing medical records.

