## Planned Analyses

Analyses will be conducted in Year 5. To evaluate Aim 1(a), we will use factorial logistic regression to test whether rates of having completed any HIV test over the 12 month study period (assessed via self-report and/or clinic records) differ by study condition. Condition, study site (and their interaction) and other relevant covariates will be entered as predictors, allowing us to explore whether each condition's effects differ by study site. To explore the effects of study condition on regular HIV testing, we will use a generalized estimating equation (GEE) for repeated, binary outcomes, specifying whether participants tested during each 3-month study period as the focal outcome. A logit link function and independent correlation structure will be specified, with study condition, site, and relevant covariates as predictors, to test whether the odds of testing differ across time period, condition, and site. GEEs are a fitting approach for studies in which correlations between repeated measures variables are to be controlled, rather than a central focus of the analysis. For all models of **HIV testing** outcomes, a covariate reflecting whether a given participant had initiated PrEP (and when, for longitudinal models) will be added to each model, since these individuals are required to test for HIV quarterly as a part of ongoing PrEP care. Doing so will allow us to estimate the effects of study arm on HIV testing among those who did not initiate PrEP. Given that we have proposed collecting 54 more participants per site (162 total) than is required to estimate our most complex model (see Model 1b in Section 3C.3.10), we believe we will be fully powered to test this model, even with a high rate of PrEP adoption. While contamination of the control group in our pilot study was rare (only one control participant reported using a HBST), we will also track **where** each participant tested (at home, in person) in quarterly surveys. If contamination is significant, we will employ methods aimed at reducing this bias, including adding indicators of contamination as covariates or bootstrapping. To evaluate Aim 1(b), we will generate variables reflecting whether participants received testing for other STIs or risk reduction counseling during each of the four 3-month intervals of the study period. Similar GEE models will be estimated for these outcomes with time period, condition, and site as predictors, to test whether the odds of receiving each service differ across these factors. To evaluate Aim 2, we will code variables indicating whether participant reports or clinic records reflect participants having consulted with a medical provider about PrEP and/or received a PrEP prescription any time across the study period. Factorial logistic regression with study site, condition, and their interaction will be entered as predictors of this outcome, to test whether the odds of having received consultation and/or a PrEP prescription differ across each of the study sites and conditions. Overall, data from those who drop out or withdraw from the study will be used in these analyses, in intent-to-treat (ITT) fashion. Similarly, we will assume values of zero for all outcomes (i.e., non-receipt of testing or services) when quarterly assessments are missing but participants are retained in the study. Depending on the degree of missing assessments, we will use multiple imputation for these values, since data from missing assessments will likely be missing not at random.

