work statements provide useful guidance for ensuring the security of health-related data that is collected, stored, and transmitted using web-based tools. As such, we will ensure that all components are developed to comply with these requirements (including the HIPAA Security Rule) for electronic protected health information and other health data. The web and mobile applications will be part of a complex web-based architecture in which all staging components (onboarding web app, participant-side web portal, administrator portal, and mobile app) interact with a centrally-hosted database. The web application will be used to collect self-report and registration data during the screening process (contact, login information). Registration data (current contact information and preferences) can be updated by participants at any time throughout the study by logging in to the secure web portal or the mobile app (for eTEST condition participants). An admin panel of the web application will also be used by study test counselors to log data from post-test counseling phone calls, including testing date, time, and results, referral information provided. The mobile application will be used to collect and relay sensor and device data, user preferences, to provide interactive information about prevention services (e.g., HIV testing, HBST, STI testing, safe sex, PrEP). Both applications are currently hosted locally (on Brown University's servers), ensuring that they are protected by Brown's strict security policies. These policies include server-specific firewalls, restricted access through a virtual private network, IP-specific verification, and encryption (both at rest and in transit). These servers are maintained by IT staff that also provide regular, secure backups, and control physical access via badge entry and sign-in with video surveillance. Together, these specifications ensure that only essential research staff have access to the data that are collected and stored by these tools.

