identify for the purposes of verifying service receipt and collecting limited clinical data (e.g., HIV/STI test results, and if positive, CD4 counts and viral loads). Quarterly online surveys will ask participants to name the specific clinics where they received each of the services that the questionnaires inquire about, and site-specific RAs will then request records from these clinics for these participants. Site-specific RAs will download participant data to explore service utilization and compile lists of participants who noted receiving services at each clinic. RAs will then contact each clinic that a participant utilized for HIV/STD testing. Once clinic data is received, site-specific RAs will code it using participants' unique study ID numbers and store it in password-protected files on Brown University's secure servers.

We realize that not all services will be verifiable (e.g., anonymous HIV testing), and that some participants may not be comfortable signing broad releases for their medical information. We also acknowledge that requiring the release of personal medical data may serve as a barrier to enrolling for some participants. At the same time, we also believe it is important to collect more objective data that can serve as a compliment to self-report whenever possible. Given these considerations, returning a signed release will not be required in order to enroll in the study, to prevent this procedure from acting as an impediment to enrollment. Instead, we will verify clinical service information for those who return their releases and consent to this specific procedure. This approach will allow us to verify as much clinical service data as possible, while minimizing participant discomfort with the study's procedures. While this likely means that data on clinical service use will be incomplete, we do not believe that incorporating this procedure undermines the importance of self-report data or the study as a whole. (See Section B4 for a full list of data collected from clinics.)

\*Data Use Agreements will be put in place to allow staff at each study site access to the study database (saved on Brown's servers) in order to verify service use and enter data collected.

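### Aim 2 scoring does not exclude PrEP events learned only from eTEST counselor calls, a route the other two arms lack

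*Combined protocol and SAP*

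**What the plan says.** **Outcome rule.** For Aim 2, Planned Analyses states that "we will code variables indicating whether participant reports or clinic records reflect participants having consulted with a medical provider about PrEP" or having received a prescription, at any time in the study. One positive source is enough. Reports are not limited to surveys, and records are not limited to those requested for a particular reason.

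**Routes common to all arms.** The quarterly survey asks everyone about PrEP consultation, the provider and any prescription (B.4, Quarterly online questionnaires). Clinic records are reviewed in every arm, PrEP uptake included (B.4, Clinic records). B.5.1.4 describes the mechanism: participants name clinics in the survey, and "site-specific RAs will then request records from these clinics for these participants". Verification depends on consent and a returned release.

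**Route in eTEST only.** "PrEP education and counseling will take place at each post-test phone call with participants in the" eTEST condition (B.4, Procedure). Those who showed interest at an earlier call are asked whether they made an appointment, "initiated PrEP, and have attended follow-up appointments, which will be corroborated by reviewing medical records". The section adds that "Counselors will record data during each call in the study database". For standard HBST, Experimental Conditions says the kits "will not be monitored and no follow-up calls will be provided"; control participants receive text reminders.

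**Missing surveys.** Planned Analyses scores a missing assessment as no event for participants who are retained, with multiple imputation possible depending on how much is missing.

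**The concern.** An either-source rule is fair between arms only if the arms have the same sources. Here eTEST has one more: a counselor who knows the assignment and delivers the PrEP intervention asks again about PrEP uptake, and the answer leads to a check of medical records. An eTEST participant who omits a visit from the survey, or misses the survey, could still be scored positive through the call. A comparable participant elsewhere has to be found through the survey or the records it prompts.

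Two features make this more than a formality. The survey's PrEP consultation item looks back one month although the survey is quarterly, and the provider and prescription questions follow only from a positive answer. The common route may therefore miss events even when surveys are completed, whereas no look-back limit is stated for the call questions. PrEP initiation is also a covariate in every HIV testing model, so unequal ascertainment would reach Aim 1 as well.

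At stake is the Aim 2 odds ratio: part of an apparent eTEST effect on PrEP uptake could come from better detection.

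**Working it through.** The plan states no figure on this point, so there is none to reproduce. The check has two parts.

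**1. Routes into the Aim 2 variable**

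| Route | eTEST | Standard HBST | Control |
|---|---|---|---|
| Quarterly survey | yes | yes | yes |
| Clinic records from survey-named clinics | yes | yes | yes |
| Counselor call asking about PrEP uptake | yes, if interest was voiced earlier | no | no |
| Record check of call answers | yes | no | no |

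Planned Analyses excludes none of the four rows. An added source under an either-source rule cannot remove an event, so the last two rows can only raise the eTEST rate.

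**2. Illustrative size when there is no true effect**

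Inputs from the documents: N = 2000 (B.4, B.5) and alpha 0.05 (Power Considerations).

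Assumptions:
- equal allocation (no ratio is stated), so 2000/3, about 667 per arm;
- a two-sided test of eTEST against one other arm, as a simplification of the planned logistic model;
- true rate p = 0.10 in both arms;
- s = share of events captured by the common routes;
- c = share of the remaining events recovered only through calls, set to 0.5.

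The value s = 0.94 borrows the pilot's average monthly survey completion. That is completion, not event capture, so it is an optimistic anchor. The values 0.85 and 0.70 are assumptions.

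Formulas:
- recorded rate, other arm = p × s
- recorded rate, eTEST = p × [s + (1 − s) × c]
- SE = √[2 × m × (1 − m) / 667], where m is the mean of the two recorded rates
- type I error = P(Z > 1.96 − d/SE) + P(Z < −1.96 − d/SE), where d is the difference in recorded rates

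Worked case, s = 0.70: other arm 0.10 × 0.70 = 0.070; eTEST 0.10 × (0.70 + 0.30 × 0.5) = 0.085; d = 0.015; m = 0.0775; SE = √(2 × 0.0775 × 0.9225 / 667) = 0.0146; d/SE = 1.02; type I error = 0.176.

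| s | eTEST | Other arm | Ratio | Type I error |
|---|---|---|---|---|
| 0.94 | 9.70% | 9.40% | 1.03 | 0.054 |
| 0.85 | 9.25% | 8.50% | 1.09 | 0.077 |
| 0.70 | 8.50% | 7.00% | 1.21 | 0.176 |

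Sensitivity, one input changed at a time (s = 0.94 / 0.85 / 0.70):
- c = 0.25: 0.051 / 0.057 / 0.082
- c = 0.75: 0.059 / 0.110 / 0.324
- p = 0.04 (the pilot control rate): 0.051 / 0.060 / 0.097
- p = 0.25 (the pilot eTEST consultation rate): 0.062 / 0.131 / 0.410
- 300 per arm (the 300 per site in Power Considerations, 3 × 300 / 3): 0.052 / 0.062 / 0.105

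With c = 0, which is what the fix achieves, the ratio is 1.00 and type I error is 0.05 throughout.

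**The case against.** The strongest reply is that the plan already means the surveys. The Overview of Research says all participants report key outcomes in quarterly questionnaires, confirmed from clinical records where possible, and Design Considerations names the online surveys as the way key self-report outcomes are assessed. No section says call logs feed the Aim 2 variable. The description of the administrator panel in B.5.1.1 says counselors will "log data from post-test counseling phone calls, including testing date, time, and results, referral information provided"; PrEP initiation is not in that list.

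The call route is also narrow. It needs a detected kit opening and interest voiced at an earlier call. With four kits and the first call given to education, at most three later calls remain. The other arms have ways to recover events too. The outcome covers the whole study, so one missed survey does not force a zero. Multiple imputation may replace zeros. A clinic named for an HIV test can yield a PrEP entry, because the extracted fields include it. The survey also asks whether each test since the last assessment was linked to PrEP care.

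All of this stands, and it limits the point. It does not close it. The passages on surveys concern self-report, while the outcome rule has a second limb, clinic records. A record located because of a call answer is a clinic record and meets the rule as written. The record check of call answers may be the same review that B.5.1.4 describes, but the text does not say so.

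Three stronger readings are tempting and unsupported. A reader might infer that record review is an eTEST-only route; it applies to every arm. A reader might infer that differential ascertainment is an established feature; the documents show only that the rule leaves it open. A reader might take the one-month look-back to mean that the common routes find only a third of events; that ignores the PrEP-linked testing item and the records, so the large bias it would imply should not be claimed.

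**Conclusion.** The point holds as an open source definition. The eTEST arm has an additional way of eliciting PrEP uptake and possibly an additional trigger for record searches, and the Aim 2 rule does not keep either out. If they are used, the direction is certain and favours eTEST.

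The size is not determinable from the documents. In the main illustration the inflation is negligible at 94% common-route capture (0.054), modest at 85% (0.077) and more than threefold at 70% (0.176). These figures rest on the assumed p, c and s, equal allocation, and a single unadjusted two-sided comparison. They also let calls recover the same share of all missed events, although only participants with prior interest who open a later kit are asked.

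**What to change.** Add to Planned Analyses, under Aim 2, wording to this effect: arm comparisons of PrEP consultation and prescription use only sources collected identically in all arms, namely the quarterly surveys and clinic records requested because of a survey report; answers given in counselor calls, and record checks prompted by them, do not contribute to the outcome. Apply the same rule to the PrEP-initiation covariate in the HIV testing models.

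Keep call answers and call-triggered record checks for process, fidelity and validation reporting. Reporting how many eTEST events were known only from calls would show how much the restriction mattered.

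The cost is a change of analysis wording and a note, for each record request, of what prompted it. No clinical procedure changes. The downside is small: true eTEST events known only from calls are not counted, as comparable unreported events in the other arms are not. If the sponsor already intends this, the sentence simply records it.

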## Planned Analyses

Analyses will be conducted in Year 5. To evaluate Aim 1(a), we will use factorial logistic regression to test whether rates of having completed any HIV test over the 12 month study period (assessed via self-report and/or clinic records) differ by study condition. Condition, study site (and their interaction) and other relevant covariates will be entered as predictors, allowing us to explore whether each condition's effects differ by study site. To explore the effects of study condition on regular HIV testing, we will use a generalized estimating equation (GEE) for repeated, binary outcomes, specifying whether participants tested during each 3-month study period as the focal outcome. A logit link function and independent correlation structure will be specified, with study condition, site, and relevant covariates as predictors, to test whether the odds of testing differ across time period, condition, and site. GEEs are a fitting approach for studies in which correlations between repeated measures variables are to be controlled, rather than a central focus of the analysis. For all models of **HIV testing** outcomes, a covariate reflecting whether a given participant had initiated PrEP (and when, for longitudinal models) will be added to each model, since these individuals are required to test for HIV quarterly as a part of ongoing PrEP care. Doing so will allow us to estimate the effects of study arm on HIV testing among those who did not initiate PrEP. Given that we have proposed collecting 54 more participants per site (162 total) than is required to estimate our most complex model (see Model 1b in Section 3C.3.10), we believe we will be fully powered to test this model, even with a high rate of PrEP adoption. While contamination of the control group in our pilot study was rare (only one control participant reported using a HBST), we will also track **where** each participant tested (at home, in person) in quarterly surveys. If contamination is significant, we will employ methods aimed at reducing this bias, including adding indicators of contamination as covariates or bootstrapping. To evaluate Aim 1(b), we will generate variables reflecting whether participants received testing for other STIs or risk reduction counseling during each of the four 3-month intervals of the study period. Similar GEE models will be estimated for these outcomes with time period, condition, and site as predictors, to test whether the odds of receiving each service differ across these factors. To evaluate Aim 2, we will code variables indicating whether participant reports or clinic records reflect participants having consulted with a medical provider about PrEP and/or received a PrEP prescription any time across the study period. Factorial logistic regression with study site, condition, and their interaction will be entered as predictors of this outcome, to test whether the odds of having received consultation and/or a PrEP prescription differ across each of the study sites and conditions. Overall, data from those who drop out or withdraw from the study will be used in these analyses, in intent-to-treat (ITT) fashion. Similarly, we will assume values of zero for all outcomes (i.e., non-receipt of testing or services) when quarterly assessments are missing but participants are retained in the study. Depending on the degree of missing assessments, we will use multiple imputation for these values, since data from missing assessments will likely be missing not at random.

**Cost-effectiveness analyses (CEA).** To examine the cost effectiveness of each condition under various scenarios (e.g., population prevalence/incidence, with/without follow-up for specific users, retesting intervals, purchase price), we will use mathematical models similar to those used in past CEA studies of HIV testing strategies. In CEA, a strategy is considered cost-

effective if the gains in health justify the resources needed to implement the program. The basic element of CEA is the incremental cost-effectiveness ratio, or the difference in the total costs associated with a given testing program versus an alternative, over the difference in incremental health improvement conferred by each program, generally measured in Quality Adjusted Life Years (QALYs). While HIV testing programs can lead to increased costs because treatment can begin earlier and continue for longer, these costs can be offset by lower rates of hospitalization and treatment for opportunistic infections, and more QALYs. To evaluate Aim 3, we will calculate the total annual costs associated with providing each HBST condition (standard and eTEST), including the costs of tests, postage, sensors, web development/maintenance, counselor resources, training, and supervision. Some of these costs depend on flexible aspects of the program, including the retesting interval (3 mos., 6 mos.), follow up strategy (only positive tests versus all tests) and purchase price. As such, we will estimate the marginal intervention costs under various scenarios to compare them with similar estimates for clinic-based, rapid HIV testing programs for MSM in high-prevalence areas from the literature. Potential health gains from testing programs include: Longer life, better quality of life, reduced risk of transmission to others among those with reactive results due to earlier awareness, diagnosis, and treatment entry, and reduced future infection risk among those testing negative by linking them with PrEP and other prevention services. These also depend on outcomes for each program, like test acceptance, the number/timing of new cases detected, rates of linkage to care and treatment initiation, and rates of linkage to other prevention services among non-infected individuals. Gains conferred by these factors will be estimated using study data and available studies to compare them with existing programs. Overall, the goal of these simulations is to arrive at an estimate of the costs associated with each HBST program under various conditions per quality-adjusted life year (QALY) gained, so that they can be compared with similar estimates for clinic-based testing programs targeting similar populations. These estimates can then be used to evaluate whether providing low or no-cost HBST (with or without follow-up) can be cost effective when targeted toward certain high-incidence populations, compared with existing clinic-based approaches.

Exploratory analyses on new HIV cases and time to diagnosis. A key advantage of achieving more frequent testing through HBST could be the ability to detect more new infections and do so earlier, ideally before disease advances and others are infected. Given this, as exploratory aims, we will also examine whether more new cases are detected, and detected earlier on, using HBST compared to relying on clinic-based testing alone. To facilitate this, all participants will be tested in-person at the conclusion of the study, to ensure that HIV test results are available for most participants, even if they elected not to test using the study interventions. Among those who did not test during the study period, new cases detected through the post-study test will suggest that the interventions likely “missed” these cases. The proportion of cases detected with study interventions versus those missed can then be compared across conditions. Confirmatory testing in those who receive a reactive test at any time during the study, together with post-study testing for all participants, will also allow us to use CD4 counts and viral loads from positive blood tests to explore differences in estimated time to diagnosis among those infected during the study period, using methods described in past studies. These aims are secondary, however, since we acknowledge that there may be insufficient numbers of those infected with HIV during the study period in each group to conduct fully-powered tests. However, based on estimates of the rate of new infections among those without an HIV diagnosis in each study site’s area, we estimate that at least 20 participants (6 per group) may

be diagnosed with HIV during the study period. This will allow some limited exploration of these aims.

**Power Considerations.** We used past studies and power estimation/ simulation packages in *R*, to determine the sample sizes necessary to detect significant effects in each of the models proposed in 3C.3.8. Relative risk ratios (RRs) were estimated for relevant outcomes (e.g., HIV testing, STI testing) across study conditions in our pilot data, and we used the smallest of these group differences for estimation so as to provide the most conservative estimate of required sample size. For each estimate, we assumed  $\alpha=0.05$ , an observed power of .80, and a small but constant effect (1.2) for study site on each outcome, to ensure that any differences emerging between study sites could be detected. For GEE models, we assumed quarterly measurements ( $T = 4$ ), with relatively independent relationships between repeated data ( $\Phi=0.2$ ). Table 2 summarizes the models, outcomes, parameters, and sample size estimates for each aim. For GEEs, sample size gives the estimated number of participants needed to test condition effects within each site. The sample size required to detect the most complex model with the smallest effects is 246. To account for missing data, we propose collecting 300 MSM at each site.

